10.3 Adjustments for Covariates

No adjustments for covariates are planned for this study.

10.4 Handling of Dropouts or Missing Data

Efficacy endpoints will be summarized by visit using OC. Additionally, efficacy endpoints will be summarized by visit using LOCF to impute missing data. LOCF will include scheduled and unscheduled visits. Baseline values will not be carried forward.

Average weekly PP-NRS scores will be calculated for all nominal visits as the average of 7 daily post-baseline PP-NRS scores prior to and including the values assessed on the visit date. If daily PP-NRS scores are missing for more than 3 days in a 7-day period, the average weekly PP-NRS score will be set to missing. If two or more scores are reported on the same day, the maximum score on that day will be used.

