4.5.1 Reasons for Withdrawal from the Study

Study drug will be discontinued and the subject withdrawn from the study for any of the following reasons:

- Subject has an AE that is considered to be related to study drug or procedures AND is severe enough to warrant treatment discontinuation, as determined by the Investigator (Section 8.1).
- Pregnancy
- Any Grade 3 or 4 AE, based on Cancer Institute Common Terminology Criteria for Adverse Events (CTCAE) criteria, considered causally related to study drug (Section 8.2.2)

Study drug may be discontinued and the subject withdrawn from the study for any of the following reasons:

- Subject requires concurrent prohibited medication during the study (Section 5.6.2). Nonmedicated emollients that do not contain salicylic acid may be used on nonlesional skin but the subject (or caregiver) should wait at least 30 minutes after applying study drug before applying nonmedicated emollients; emollients should not be applied to lesional skin during treatment. The same emollient should be used throughout the subject's participation in the study.

NOTE: If, in the opinion of the Investigator and the study Medical Monitor, such medication will not interfere with the conduct or interpretation of the study or compromise the safety of the subject, then the subject may continue to receive study drug.

- Subject noncompliance
- Investigator noncompliance
- Discontinuation of the study at the request of the Sponsor, regulatory agency, or an Institutional Review Board (IRB)/Independent Ethics Committee (IEC).

If a subject meets a withdrawal criterion during treatment, an Early Termination visit will be required (Section 7.7).

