5.6.2 Prohibited Medications and Nondrug Therapies

Medications and nondrug therapies that are prohibited throughout the study duration are as follows:

- DUPIXENT® (dupilumab) injection, or any monoclonal antibody product that becomes approved for AD during the course of the trial
- Oral, injectable, and suppository preparations of corticosteroids. Eye drops and nasal preparations are allowed. Inhaled preparations are allowed when used for a stable condition and stable dose for > 28 days before Baseline and are continued at the same dose throughout the study.
- Oral preparations and injections of immunosuppressants (cyclosporine, methotrexate, azathioprine, tacrolimus, JAK inhibitors, etc.).
- Excessive sun exposure, tanning booth, other ultraviolet light source and phototherapy including psoralen and ultraviolet A therapy or is unwilling to minimize natural and artificial sunlight exposure.
- Treatment with antivirals with the exception of short-term treatment for acute upper respiratory viral infections (i.e., influenza) or viral suppressive therapy for a history of recurrent herpes labialis or genital herpes.
- EUCRISA® (crisaborole) and any other phosphodiesterase 4 inhibitor.
- Tacrolimus ointment and pimecrolimus cream.
- Topical JAK inhibitors.
- Topical corticosteroids that are classified as low potency (e.g., desonide, hydrocortisone), medium or high potency (e.g., fluocinonide, triamcinolone acetonide) or super-high potency (e.g., clobetasol propionate). Eye drops and nasal preparations are allowed.
- Over the counter or herbal medicines for AD (topical and oral preparations). If subjects are using emollients, they may continue to use the same emollient on nonlesional skin during the study. Emollients containing salicylic acid are prohibited during the study.
- Oral, injectable, or intravenous antibiotics or antifungal medications.
- Topical doxepin or topical antibiotics.

NOTE: Oral doxepin is allowed for treatment of depression if subject has been on a stable dose (4 weeks) at Screening

- Antihistamines/antiallergics (oral, topical and injections): diphenhydramine, chlorpheniramine maleate, hydroxyzine.

NOTE: The following antihistamines are allowed from Screening throughout the treatment period: loratadine, fexofenadine hydrochloride, cetirizine hydrochloride. Subjects are allowed to switch from non-allowed antihistamines to allowed antihistamines during Screening but must be on a stable dose for 7 days prior to Baseline.

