10.6 Handling of Missing Data

Summaries of efficacy endpoints by visit will be performed using OC and LOCF methods.

11 Responsibilities

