Efficacy and safety endpoints will be summarized according to the nominal visit as assigned by the investigator except for assessments collected on early termination visits. Early termination visit will be assigned based on the last nominal visit across all procedures and assessments and re-numbered to the last nominal visit number + 1. For example, if a subject attended Visit 1 (Baseline), Visit 2 (Week 4), Visit 3 (Week 8) and then early terminated, the early termination visit will be re-numbered and analyzed as Visit 4 (Week 12).

Unscheduled visits will not be re-numbered and will not be included in OC summaries but will be included in listings. Unscheduled visits will be included in the LOCF imputation by using

target day listed in the Visit Terminology table; for missing visits LOCF values will be based on scheduled and unscheduled visits occurring on or before target day.

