8. ANALYSIS SETS

The following subject population will be used for safety and efficacy analyses:

- The intent-to-treat (ITT) population will include all subjects enrolled into the study.

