10.1 Efficacy Variables

[figure not shown]
Efficacy endpoints

For subjects entering the study with a vIGA-AD™ score ≥ 1 :

- Proportion of subjects who achieve vIGA-AD™=0 at least 1 time on or before Week 48
- [REDACTED]
- [REDACTED]
- [REDACTED]
- [REDACTED]

For subjects entering the study with a vIGA-AD™ score ≥ 2 :

- [REDACTED]
- [REDACTED] change and percent change from Baseline in %BSA affected by visit (OC and LOCF)
- [REDACTED]
- [REDACTED] change and percent change from Baseline in EASI score by visit (OC and LOCF)
- Proportion of subjects with $\geq 50\%$ improvement in EASI score from Baseline by visit (OC and LOCF)
- Proportion of subjects with $\geq 75\%$ improvement in EASI score from Baseline by visit (OC and LOCF)
- Proportion of subjects with $\geq 90\%$ improvement in EASI score from Baseline by visit (OC and LOCF)
- Mean change in average weekly PP-NRS score from Baseline at each study visit (OC and LOCF)
- Proportion of subjects with a Baseline PP-NRS score ≥ 4 who achieve ≥ 4 -point reduction in the average weekly PP-NRS from Baseline at each study visit (OC and LOCF)

- [REDACTED]

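### The readable plan has no rule for efficacy values recorded after a subject starts a prohibited atopic dermatitis therapy, so they enter the response summaries as if obtained on tapinarof alone

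*SAP*

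**What the plan says.** - **Prohibited therapy.** Protocol 5.6.2 bars other AD treatment for the whole study. The list includes topical corticosteroids of every potency, topical calcineurin inhibitors, systemic immunosuppressants and "DUPIXENT® (dupilumab) injection, or any monoclonal antibody product that becomes approved for AD during the course of the trial".
- **Consequence of use.** Protocol 4.5.1 puts need for a prohibited medication among the reasons for which a subject may, not must, be withdrawn. If the Investigator and Medical Monitor judge that the medication will not affect study conduct, interpretation or safety, "then the subject may continue to receive study drug".
- **Analysis set.** SAP 8 has one set: "The intent-to-treat (ITT) population will include all subjects enrolled into the study".
- **Missing data.** Protocol 10.6 reads in full: "Summaries of efficacy endpoints by visit will be performed using OC and LOCF methods". SAP 10.4 adds the LOCF rule: "Additionally, efficacy endpoints will be summarized by visit using LOCF to impute missing data. LOCF will include scheduled and unscheduled visits". Neither is conditional on other therapy.
- **Early termination (ET) visit.** Protocol 7.7 has vIGA-AD, %BSA, EASI and PP-NRS scored there. SAP 7 says "Early termination visit will be assigned based on the last nominal visit across all procedures and assessments" and then moves the visit up by one number, so it is analysed as the next scheduled visit.
- **Ever-clear endpoint.** SAP 10.1 defines "Proportion of subjects who achieve vIGA-AD™=0 at least 1 time on or before Week 48" with no visible condition on concomitant therapy.
- **Medication and deviation data.** SAP 9.5 lists and tabulates concomitant medications, and SAP 9.2 does the same for protocol deviations. No readable text links either to an efficacy value.

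**The concern.** This is a single-arm study without testing, so the descriptive rates are the efficacy result. Protocol section 10 says the study is meant to show a favourable safety and efficacy profile, and protocol 10.5 plans a data cut for the marketing application. With no control group in which other therapy would also appear, its effect cannot be separated from that of tapinarof.

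A subject who clears after starting a topical steroid would meet the ever-clear definition. A subject off study drug who holds off a flare with a prohibited product would look like a case of maintained control. One such score can also count twice: under protocol 5.1.5.1 a vIGA-AD of 0 ends the treatment course and starts remission monitoring, so it can feed both the clearance and the disease-control results.

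**Working it through.** **The plan's own figure.** There is no power or event calculation to reproduce. The only stated number is maximum enrolment: 836 + 125 = 961, which agrees. It is used below only to turn percentages into subjects.

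**How a value recorded after the start of a prohibited therapy reaches the tables**

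1. *Subject stays on study.* Later visits are observed, so they enter the OC summaries and the EASI-50/75/90 and PP-NRS responder counts. LOCF plays no part.
2. *Ever-clear.* A single vIGA-AD of 0 by Week 48 is enough. Again LOCF plays no part.
3. *Use found only at the visit.* Scheduled visits are four weeks apart, and the schedule of assessments collects concomitant medications and vIGA-AD at the same visit. A therapy started in between can therefore come to light when its effect is already being scored. A later decision under protocol 4.5.1 does not remove that score.
4. *Subject leaves.* The ET value is renumbered and LOCF carries it on. In the SAP 7 example (last visit Week 8, ET analysed as Week 12), it would also fill Weeks 16, 20, 24, 28, 32, 36, 40, 44 and 48, which is nine further visits. SAP 10.6 names Week 48 LOCF outcomes for vIGA-AD, %BSA and EASI.
5. *Subject off study drug.* The endpoint of never reaching vIGA-AD 2 or more is in protocol 10.4.2, and SAP 11.1 mentions time to first worsening. The SAP derivation of these is not visible, so this route is open rather than shown.

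**Size, under assumptions.** The documents give neither the rate of use nor response among users. Two different quantities can be illustrated.

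*Upward bias* = u × d, where u is the share of subjects using such therapy and d is the added probability of a counted response:

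| u | d | Bias |
|---|---|---|
| 5% | 20 points | 0.05 × 0.20 = 1 point |
| 10% | 40 points | 0.10 × 0.40 = 4 points |
| 15% | 60 points | 0.15 × 0.60 = 9 points |

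*Change in the reported rate if responses after the start are not counted* = u × r, where r is the share of users whose only counted response came after the start:

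| u | r | Change | Subjects, of 961 |
|---|---|---|---|
| 2% | 30% | 0.6 points | 5.8 |
| 10% | 50% | 5.0 points | 48.1 |
| 20% | 70% | 14.0 points | 134.5 |

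In the middle row, if non-users respond at 50%, the planned rate is 0.90 × 50% + 0.10 × 50% = 50.0%, and the rate with users as non-responders is 0.90 × 50% = 45.0%. The subject counts are upper figures: 961 is a maximum, and some endpoints exclude subjects who enter clear.

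The two tables answer different questions, so neither corroborates the other.

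**The case against.** **Silence in a redacted document.** No sentence says that these values count as tapinarof response. SAP 13.1 refers to treatment-period definitions in SAP 10.1 that cannot be seen, so working rules did sit in the hidden text. This stands as a limit on certainty. The general sections where such a rule belongs (SAP 8, SAP 10.4, protocol 10.6) are readable and have none.

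**The 4.5.1 test.** A reader might infer that subjects can simply stay in the study on dupilumab or a potent steroid. The text does not support that: continuation depends on two parties judging that interpretation is unaffected. This narrows the problem. It does not close it, because the test decides who continues study drug, not which scores are analysed, and withdrawal is optional.

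**LOCF.** It is tempting to see LOCF as the main fault and carried ET values as always favourable. Neither follows. LOCF fills only missing visits, and the observed-case and ever-clear routes do not need it. A subject who leaves in flare before the other therapy works carries a poor score forward. The ET route inflates results only when scoring follows effective therapy.

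**Choice of estimand.** Summarising all observed data whatever else was used is a recognised treatment-policy approach, and affected subjects could be traced from the listings. This stands as a reason to keep those tables. It does not excuse leaving the choice unstated.

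**Conclusion.** The gap is real in the readable text. Values recorded after a prohibited AD-directed therapy starts are not set apart, and as written they enter the OC summaries, the ever-clear and EASI/PP-NRS responder endpoints and, for subjects who leave, the Week 48 LOCF summaries. Where the other therapy works, the tendency is towards better response and disease-control figures.

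The conclusion assumes that the redacted parts of SAP 10.1 and 11.1 contain no rule of their own. The size is unknown, and the range of 1 to 9 points should not be read as an estimate. The harm is to the interpretation of descriptive rates; there is no type I error to inflate. The plan should be changed, but the all-observed analysis need not be replaced.

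**What to change.** Add to SAP 10.4, before database lock:

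- By medical review of the concomitant-medication data, flag each AD-directed therapy listed in protocol 5.6.2, with its start date.
- Keep the all-observed ITT tables and state that they include values under other therapy.
- Add one pre-specified analysis in which, from the start of the flagged therapy:
  - (a) later values do not count as response for the ever-clear, EASI-50/75/90 and PP-NRS endpoints, while clearance reached before the start still counts;
  - (b) for continuous summaries, later values, including the ET value, are set to missing and are not an LOCF source;
  - (c) for the never-worsened and time-to-worsening endpoints, the start counts as loss of control, unless the redacted derivation already handles it.
- Say openly that (a) and (b) target different estimands: (b) lets LOCF carry a score from before the therapy, which may be a good one, for a subject whom (a) treats as a non-responder.
- Pre-specify how long the flag lasts for each therapy class. The periods in exclusion 13 (7, 14 or 28 days, or 4 months) may be borrowed as an analysis assumption. They are pre-Baseline eligibility windows for direct-enrolling subjects, not on-study washouts, and the SAP should say so.
- Report the number of subjects affected.

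The change is analytic only and does not alter care. It costs SAP wording, a review of medications already coded and one extra set of tables, and response figures in the added analysis may be slightly less favourable. If use proves rare, the added tables will show that too.

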PP-NRS (pre-dose) ^p		X	X	X	X	X	X	X	X	X	X	X	X	X	X	
Photograph of disease area ^r				X			X			X			X			

Procedures and Assessment	Long-term Extension Period for All Subjects														FU	ET ^v
	P/C ^w	V 2	V 3	V 4	V 5	V 6	V 7	V 8	V 9	V 10	V 11	V 12	V 13	V 14	NA	
	Week 2	Week 4	Week 8	Week 12	Week 16	Week 20	Week 24	Week 28	Week 32	Week 36	Week 40	Week 44	Week 48	Week 49	NA	
Day 15 (±3 days)	Day 29 (± 3 days)	Day 57 (±3 days)	Day 85 (±3 days)	Day 113 (±3 days)	Day 141 (±3 days)	Day 169 (±3 days)	Day 197 (±3 days)	Day 225 (±3 days)	Day 253 (±3 days)	Day 281 (±3 days)	Day 309 (±3 days)	Day 337 (±3 days)	Day 344 (±3 days)	NA		
Adverse events	X	X	X	X	X	X	X	X	X	X	X	X	X	X	X	X
Concomitant medication	X	X	X	X	X	X	X	X	X	X	X	X	X	X	X	X
Dispense (D) /collect (C) diary ^p		C/D	C/D	C/D	C/D	C/D	C/D	C/D	C/D	C/D	C/D	C/D	C		C	
Review diaries for treatment compliance		X	X	X	X	X	X	X	X	X	X	X	X		X	
Dispense (D) /collect (C) study drug ^s		C/D	C/D	C/D	C/D	C/D	C/D	C/D	C/D	C/D	C/D	C/D	C		C	
Review instructions for study drug application ^t	X	X	X	X	X	X	X	X	X	X	X	X				
Study drug application under supervision ^u		X	X	X	X	X	X	X	X	X	X	X				

a. Baseline Visit to occur at the time of completion of Visit 6 (Week 8) from the DMVT-505-3101 or DMVT-505-3102 studies. Assessments with an unbracketed X should be completed at the Baseline visit. For assessments with a bracketed X, the assessment completed at the final visit of the parent study will be used as the Baseline value for this study.

b. Baseline Visit to occur at the time of completion of Visit 4 (Day 28) from the DMVT-505-2104 study. Assessments with an unbracketed X should be completed at the Baseline visit. For assessments with a bracketed X, the assessment completed at the final visit of the parent study will be used as the Baseline value for this study.

c. Demographics/Fitzpatrick skin type as collected at Screening in one of three parent studies (Phase 3 pivotal safety and efficacy study DMVT-505-3101, Phase 3 pivotal safety and efficacy study DMVT-505-3102, or Phase 2 maximal use PK study DMVT-505-2104).

d. Review medical history as collected in one of three parent studies.

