e. Medical history will include year of AD diagnosis, CV family history, allergic conditions, and risk factors (including height, weight, medical conditions) and family history of liver disease. As part of the subject's medical history, all systemic (oral and injectable) medications used by the subject for treatment of AD prior to 30 days before the Screening visit will be collected.

f. Review medical history at Baseline and record any changes.

g. Physical examination will include height and weight (BMI will be calculated in the CRF) at the Screening visit; a brief physical examination will be performed at other visits.

h. Vital signs will include blood pressure, pulse rate, and body temperature and should be measured after the subject is seated for at least 5 minutes. Vital signs will be measured before blood collection for clinical laboratory assessments (where applicable).

i. Serum pregnancy test to be performed at the Screening visit only and urine pregnancy test to be performed at subsequent clinic visits when pregnancy testing is performed.

j. Urine pregnancy test to be performed before randomization.

k. Includes serum chemistry and liver chemistry tests, and hematology.

l. Blood sample collection for clinical laboratory tests is not required at the Baseline Visit if it has been ≤14 days since samples were collected at Screening and the results of those clinical laboratory tests were within the normal range.

m. Urine sample collection for urinalysis is not required at the Baseline Visit if it has been ≤14 days since samples were collected at Screening and the results of those clinical laboratory tests were within the normal range.

n. The vIGA-ADTM assessment should be performed before the %BSA and EASI assessments. The subject's scalp should be excluded from the vIGA-ADTM, %BSA, and EASI calculations.

p. Subjects (or caregivers) should perform the PP-NRS assessment daily and record the results in their diary. When subjects apply study drug in the clinic, subjects will not complete the diary at home; application time and PP-NRS will be recorded in the clinic. PP-NRS should be completed every day, even if subjects are not actively applying study drug.

r. Photography will be performed in a subgroup of subjects at selected study sites. Informed consent/assent and photographic release will be required.

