6.3.2.3 Peak Pruritus-Numeric Rating Scale

The PP-NRS is a scale used to quickly assess itch/pruritus severity over a 24-hour period. The subject or caregiver will utilize the scale to assess peak pruritus QD and record the results in their daily diaries. The itch

rating can be done before or after study drug administration since it should reflect the past 24 hours. On clinic visit days, the PP-NRS will be assessed in the clinic. PP-NRS should be completed every day, even if subjects are not actively applying study drug. For subjects ages 2 to < 12 years, the PP-NRS will be completed by the caregiver. For subjects ages \geq 12 years, the PP-NRS will be completed by the subject.

An example of the PP-NRS is provided in [Appendix 13](#).

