7.5 Follow-Up Visit 14; Week 49 (Day 344 ±3 Days)

Subjects will return to the study site 1 week (± 3 days) after last treatment to complete follow-up assessments as follows:

- Brief physical examination
- Vital signs measurement
- Blood sample collection for clinical laboratory tests (serum chemistry and hematology)
- Urinalysis
- vIGA-AD™ score (excluding subject's scalp)
- %BSA affected calculation (excluding subject's scalp)
- EASI (excluding subject's scalp)
- [REDACTED]
- [REDACTED]
- PP-NRS (by subject or caregiver)
- [REDACTED]
- [REDACTED]

- AE recording
- Concomitant medication recording

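### The diary ends at Week 48, so the Week 49 weekly PP-NRS is set to missing for most completers and its LOCF row normally repeats Week 48

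*SAP*

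**What the plan says.** **Analysis.** SAP 10.4: "Average weekly PP-NRS scores will be calculated for all nominal visits as the average of 7 daily post-baseline PP-NRS scores", the period ending on and including the visit date. The same section adds: "If daily PP-NRS scores are missing for more than 3 days in a 7-day period, the average weekly PP-NRS score will be set to missing". SAP 7 lists Week 49 (Day 344 ± 3) among the visits. SAP 10.1 summarises both the mean change in weekly PP-NRS and the proportion with a reduction of at least 4 points at each study visit, by OC and by LOCF. Under SAP 7, LOCF draws on scheduled and unscheduled visits up to the target day.

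**Data collection.** Protocol Table 1, footnote p: "Subjects (or caregivers) should perform the PP-NRS assessment daily and record the results in their diary". Section 6.3.2.3: "PP-NRS should be completed every day, even if subjects are not actively applying study drug". The Table 1 diary row reads C/D at Visits 2 to 12, C alone at Visit 13 (Week 48), blank at Visit 14 (Week 49), and C at early termination. The diary-review row likewise has no entry at Week 49. Section 7.5 asks for a PP-NRS at the follow-up visit but lists no diary to collect or review.

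**The concern.** The two sides of the plan do not fit at Week 49. The protocol asks for a score every day, but its schedule takes away the means of recording one after Week 48. The SAP then applies to Week 49 a rule that assumes a diary was kept during the preceding week.

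Two consequences follow. The OC row at Week 49 holds few subjects or none, selected by a short interval between visits. The LOCF row is filled mainly with Week 48 values, so it shows no change from Week 48 to Week 49 by construction, whatever happened to itch after the last application. Meanwhile a genuine Week 49 score, taken in clinic, is left out of the summary. Week 49 is the one scheduled visit at which every completer is off drug, so a reader might take that row as evidence about itch after stopping.

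**Working it through.** The plan gives no figure for this, so the check is a day count.

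**Inputs**
- Window: 7 calendar days ending on the visit date, at most 3 missing (SAP 10.4).
- Week 48: Day 337 ± 3. Week 49: Day 344 ± 3 (SAP 7).
- Diary: last collected at Week 48 (Table 1). It is assumed complete up to and including that visit, which is the most favourable case.
- After Week 48: one in-clinic score, at Week 49 (7.5).

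**Formula.** Let g be the number of days from the Week 48 visit to the Week 49 visit. The window runs from 6 days before the Week 49 visit to the visit itself.

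Scores available = 1 + max(0, 7 − g). The mean is computed only if this is at least 4, that is, if g ≤ 4.

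| g (days) | Scores | Missing | Result |
|---|---|---|---|
| 3 | 5 | 2 | computed |
| 4 | 4 | 3 | computed |
| 5 | 3 | 4 | set to missing |
| 6 | 2 | 5 | set to missing |
| 7 or more | 1 | 6 | set to missing |

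**On schedule.** g = 344 − 337 = 7. The window is Days 338 to 344 and holds one score, Day 344. Six are missing, so no completer has a value.

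**With visit-window spread.** The documents do not give actual visit timing, so these are assumptions.
- Gap uniform on 4 to 10 days (7 ± 3): only g = 4 passes. Set to missing: 6/7 = 86%.
- Both visits independently uniform in their ± 3-day windows: g ≤ 4 requires Week 49 to move at least 3 days closer to Week 48 in total. That happens in 4 + 3 + 2 + 1 = 10 of 49 combinations. Set to missing: 39/49 = 80%.

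Visits clustered nearer their target days than this give a share between these figures and 100%. Missed diary entries before Week 48 can only raise it.

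**Content of the values that pass.** At g = 4, three of the four averaged scores were recorded on or before the Week 48 visit, so even that mean mostly describes Week 48.

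**LOCF.** With Week 49 missing, the latest earlier value is carried, normally the Week 48 weekly mean. If that is missing too, an earlier visit is used.

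**The case against.** The case against concerns consequence and certainty rather than the count, and much of it stands.

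- **Off-drug itch is recorded elsewhere.** A reader might infer that Week 49 is the only place to describe itch after stopping. It is not. Subjects stop treatment when vIGA-AD reaches 0 and stay off until it is 2 or more (Protocol 3.1, 5.1.5.1), and daily scoring with diary exchange continues through those intervals up to Week 48.
- **The clinic score is not lost.** A reader might infer that it is thrown away. Protocol 10.1 and SAP 6 list all data by subject, so it is reported there; it is only left out of the weekly-mean summary.
- **Nearly every completer is too strong without a timing assumption.** It holds on schedule. With evenly spread visits, 14% to 20% would have a value.
- **The weight is limited.** Week 49 is a safety follow-up, the subgroup outcomes in SAP 10.6 that name a visit are set at Week 48, and nothing is tested. OC counts printed beside the LOCF row would show an attentive reader that the values are imputed.
- **Some text cannot be seen.** The visible part of 7.3 stops before any diary items, and SAP 10.1 and 11 are heavily redacted. Some Table 1 cells also sit uneasily with 7.3 (laboratory tests at Week 48). The diary reading does not rest on one cell, however: the diary row, the diary-review row and 7.5 agree.

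A diary might also be issued at an unscheduled visit (7.6), but that would be an exception. None of this supplies a valid weekly mean at Week 49 under the visible rules.

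**Conclusion.** The point holds in a limited form. On the visible text, the Week 49 weekly PP-NRS is set to missing whenever the gap from Week 48 is 5 days or more: all completers on schedule, and about 80% to 86% under evenly spread visits. The LOCF row then normally repeats Week 48, for both the mean change and the 4-point responder proportion.

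Only the Week 49 row of descriptive PP-NRS summaries is affected. Week 48 and earlier rows stand, and early terminators are not affected in this way because their diary is collected at the termination visit. The documents do not support reading this as a loss of all off-drug itch data or as a threat to the study's main results. The verdict rests on the Table 1 diary row as read here and on there being no Week 49 rule in redacted or unseen text. It still deserves correction, because the plan would print a row that cannot show change from Week 48 for most subjects while omitting from the summary a score already collected.

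**What to change.** **In SAP 10.1 and 10.4:** at Week 49, summarise the single in-clinic PP-NRS as change from Baseline, OC only, and derive the 4-point responder proportion from it. Produce no LOCF row for PP-NRS at Week 49. The single Week 48 clinic score may be shown alongside. This matches Protocol 10.4.2, which words the endpoint by visit without weekly averaging. It is also like-for-like for rollover subjects, whose Baseline under SAP 10.2 is normally one visit score.

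**If data collection is still open:** reconcile the Table 1 diary row and section 7.5 with footnote p and 6.3.2.3, by making the entry C/D at Week 48 and C at Week 49. Up to 7 of 7 scores would then be available at any gap. The SAP is dated 21APR2023 against a protocol of 16JUN2021, so this may come too late.

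**Cost:** a short SAP change, or one more diary and a week of itch entries per completer. The drawback of the SAP route is that a single-day score is noisier than a weekly mean and not on the same footing as the weekly means in the other rows, so the table should say so in a footnote.
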